#### 3.1.1 Study Schema

Version Date: January 24, 2017

### 3.2 DRUG ADMINISTRATION

## 3.2.1 Clobetasol Administration

Clobetasol 0.05% oral rinse and placebo rinse which will be identical in appearance and taste will be labeled and dispensed by the NIH Clinical Center Pharmacy. Subjects will be instructed to rinse oral cavity 3 times daily with the 10 cc of the study medication for 2 minutes and spit out and not to eat, drink, or brush teeth for 30 minutes after the study drug administration. Additionally, the use of oral topical analgesic (viscous lidocaine) will not be allowed for 30 minutes before and after study drug administration.

## 3.2.2 Duration of Drug Therapy

Patients will be treated with study medication for up to 4 weeks initially. If patients enter the continuation treatment period, they can be treated for up to an additional 4 weeks. Patients may be allowed to enter the continuation treatment period up to 90 days after the last day of treatment.

## **3.2.3 Progressive disease**

Patients with progressive oral cGVHD after 2 weeks of treatment with the clobetasol oral rinse will be taken off study. See also Section **6.3.1**.

## 3.2.4 Treatment after 2 week blinded phase

Patients who switch to the clobetasol arm due to initial placebo assignment will be treated with clobetasol 0.05% oral rinse for 4 weeks. Patients originally assigned to clobetasol arm will be treated for another 2 weeks.

#### 3.3 TREATMENT MODIFICATIONS

All dose modifications must be discussed with the PI, or LAI. Given favorable toxicity profile of clobetasol, no treatment modifications are expected. Grade 2 – 3 CTCAE v.4 events attributable to underlying disease and occurring prior to administration of clobetasol will not be reported as an adverse event. These physical findings must be documented at baseline. Expected pre-existing manifestations of cGVHD or systemic steroid therapy may include the following examples: fatigue, colitis, cushingoid appearance, anorexia, dyspepsia, xerostomia, parotid swelling, nausea, taste alteration, arthritis, fibrosis, myositis, osteonecrosis, osteopenia, dry eye, watery eye, pain, dyspnea, vaginal dryness, skin atrophy, alopecia, hyperpigmentation, skin dryness, hypopigmentation, nail changes, photosensitivity, pruritus, rash, and ulcers. In the event of grade 2-3 adverse event attributable to study agent that cannot be easily alleviated without compromising the integrity of the study (such as severe local or systemic hypersensitivity) the subject will be taken off study and treated appropriately as detailed in Protocol Evaluations

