## **3** STUDY IMPLEMENTATION

## 3.1 STUDY DESIGN

This is a randomized, double blind, placebo-controlled, pilot study of clobetasol 0.05% topical oral rinse with an open label cross-over or extension period. Consenting subjects with clinically significant oral chronic GVHD will be randomized to clobetasol 0.05% or placebo oral rinse. The placebo will be flavored with quinine, to approximate the "bitter" taste of clobetasol.

Subjects will be evaluated at bi-weekly intervals while on the study intervention. OMRS score will serve as the primary outcome measure. At the first 2 week interim appointment patients will be unblinded and started on the clobetasol oral rinse open label. In the absence of progressive oral disease on the scheduled interim evaluations during the 4-week clobetasol treatment period, all patients will complete a total of 4 weeks of treatment with clobetasol. Therefore, patients who were originally assigned to clobetasol arm will receive additional 2 weeks of treatment, and patients assigned to placebo arm will undergo an additional 4 weeks of treatment with clobetasol after unblinding. Patients with progressive disease after 2 weeks of therapy with clobetasol will be considered non-responders, taken off-treatment and treated as appropriate in consultation with primary clinician. Within 90 days of the end of the 1 month of treatment, all patients with evidence of benefit (response or stable disease) will be given an option to continue treatment with clobetasol 0.05% with or without additional treatment as deemed clinically necessary for 1 month after the conclusion of the initial treatment period. Additional follow-up appointment will be scheduled for all patients 1 month after completion of treatment. The change in OMRS scores from baseline to 4 weeks of mouth rinse usage will be the primary outcome variable. For the placebo group, the OMRS score at the end of the blinded phase/beginning of clobetasol rinse use (day 14) will serve as the baseline for the primary outcome. Difference in OMRS score between the groups (placebo and clobetasol) at the end of the 14-day blinded phase will serve as a secondary outcome measure. The study schedule of events is outlined in Appendix G.

# 

#	Because of problems with your teeth, denture or mouth have you	Never (0)	Hardly ever (1)	Occasionally (2)	Often (3)	Very Often (4)
1	Had trouble pronouncing words					
2	Felt sense of taste has worsened					
3	Had painful aching in the mouth					

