## 8.2 Assessment of Safety Events

AE information collected will include event description, date of onset, assessment of severity and relationship to study product and alternate etiology (if not related to study product), date of resolution of the event, seriousness and outcome. The assessment of severity and relationship to the study product will be done only by those with the training and authority to make a diagnosis and listed on the Form FDA 1572 as the site Principal Investigator or sub-investigator. AEs occurring during the collection and reporting period will be documented appropriately regardless of relationship. AEs will be followed through resolution.

SAEs will be:

• Assessed for severity and relationship to study product and alternate etiology (if not related to study product) by a licensed study physician listed on the Form FDA 1572 as

the site Principal Investigator or sub-investigator.

- Recorded on the appropriate SAE report form, the medical record and captured in the clinical database.
- Followed through resolution by a licensed study physician listed on the Form FDA 1572 as the site Principal Investigator or sub-investigator.

For timeframe of recording adverse events, please refer to Section 6.1. All serious adverse events recorded from the time of first investigational product administration must be reported to the sponsor with the exception of any listed in Section 8.4.

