This study will aim to enroll a total of 34 evaluable patients randomized in a 1:1 fashion (17 per arm) to receive clobetasol rinse or placebo. The initial phase of the study will involve two weeks of either clobetasol rinse or placebo. At the end of the initial 2 weeks, patients receiving placebo will receive 28 days of clobetasol while those receiving clobetasol initially will receive an additional 14 days of clobetasol. Thus, each group will receive 28 days of clobetasol following either a 14 day placebo or immediately after randomization.

Patients will be randomized with a single stratification factor to try to ensure a balanced distribution among those getting placebo or not initially: being identified as having a high intensity of immunosuppression (2 or more agents/modalities  $\pm$  prednisone $\geq$ 0.5 mg/kg/day) vs. no or a lesser intensity of systemic immunosuppression according to the Intensity of Immunosuppression Scale . This scale was developed using expert opinion, and has been preliminarily demonstrated to have predictive validity as measure of the intensity of systemic immunosuppression. A low intensity regimen is defined as treatment with prednisone alone at a dose of less than 0.5 mg per kilogram per day. Moderately intense regimens include single agent prednisone at a dose greater than or equal to 0.5 mg per kilogram per day, and/or any other single agent or modality. Regimens comprised of two or more agents or modalities (+/- prednisone greater than or equal to 0.5 mg per kilogram per day), are categorized as highly intensive systemic immunosuppression. When scoring the intensity of systemic immunosuppression, the use of topical agents is not captured.

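### Section 3.3 ties an adverse-event exemption to first clobetasol, so read literally it exempts one class of blinded-phase events on placebo but not on clobetasol

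*Combined protocol and SAP*

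**What the plan says.** Section 3.3 (Treatment Modifications) removes a class of events from reporting: grade 2-3 CTCAE v.4 events "attributable to underlying disease and occurring prior to administration of clobetasol will not be reported as an adverse event". Two sentences qualify it. The first is "These physical findings must be documented at baseline". The second opens "Expected pre-existing manifestations of cGVHD or systemic steroid therapy may include the following examples" and lists, among others, nausea, taste alteration, xerostomia, pain, rash and ulcers.

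On timing, Section 10.2 says "The initial phase of the study will involve two weeks of either clobetasol rinse or placebo". Sections 3.1, 3.2.4 and 10.2 then give placebo-first patients 28 days of clobetasol after unblinding at the 2-week visit. Clobetasol-first patients take it from randomisation.

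Section 8.2 sets the general rule: "AEs occurring during the collection and reporting period will be documented appropriately regardless of relationship". For serious events it says "All serious adverse events recorded from the time of first investigational product administration must be reported to the sponsor". It refers to Section 6.1 for the recording timeframe. Section 6.1 holds only a rule on grade 1 events and gives no start date.

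**The concern.** The exemption is timed to one of the two study rinses instead of to the start of study treatment. In the clobetasol arm the two coincide. In the placebo arm they lie 14 days apart, and those 14 days are the whole blinded phase. A grade 2-3 event that begins on day 7 and is put down to chronic GVHD falls after first clobetasol in one arm and before it in the other.

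The blinded phase is the only period with concurrent placebo data, so any by-arm summary of adverse events has to draw on it. Several listed examples (pain, taste alteration, nausea, ulcers) are ones on which a mouth rinse might reasonably be compared with placebo. An event that started on placebo and persisted could also be treated as pre-existing for that patient's clobetasol period.

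Blinding does not remove the problem. Blinded staff cannot know whether clobetasol has been given, so they cannot apply the clause as written before day 14. It becomes applicable at the day-14 visit, where Section 3.1 places the unblinding and Appendix G places adverse-event monitoring. The reporting decision could then be made with the arm known.

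**Working it through.** No figure in the plan depends on this clause, so there is nothing to reproduce. The check is a comparison of texts, followed by an illustration of size.

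**1. Exempt window after the start of rinse, by arm (literal reading).** The window runs from first study rinse to first clobetasol.
- Clobetasol arm: day 0 to day 0, or 0 of 14 blinded days.
- Placebo arm: day 0 to day 14, or 14 of 14 blinded days.
- With 17 patients per arm (Section 10.2): 17 × 14 = 238 patient-days on placebo and 17 × 0 = 0 on clobetasol.
- If the clause were tied to the first dose of either rinse: 0 of 14 in both arms.

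**2. Does another section settle it?**
- Section 8.2 documents events whatever their cause, whereas Section 3.3 exempts by cause. The two conflict, and neither says which governs.
- Section 8.2 starts serious-event reporting at first investigational product, whereas Section 3.3 uses first clobetasol.
- Section 8.2 sends the reader to Section 6.1, which has no start date.
- Appendix G schedules adverse-event monitoring at day 14 but does not say what must be reported there.

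**3. What falls outside the clause.** Events not attributed to underlying disease, including those judged related to the rinse, related grade 1 events (Section 6.1) and grade 4-5 events are outside it. Serious events have their own start in Section 8.2.

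**4. Size, as a worst case.** The documents give no rate, so assume the same true 14-day proportion r of patients with such an event in both arms, all reported on clobetasol and none on placebo. The expected number reported on clobetasol is 17r. For a sense of scale, take a two-sided Fisher exact test at 0.05, which the plan does not call for. With 0 of 17 on placebo:
- 5 of 17 on clobetasol gives p = 2 × C(17,5)/C(34,5) = 2 × 6188/278256 = 0.044.
- 4 of 17 gives p = 2 × C(17,4)/C(34,4) = 2 × 2380/46376 = 0.103.

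Five or more reported patients would therefore produce a spurious p ≤ 0.05. The chance of that is P(Binomial(17, r) ≥ 5).

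| Assumed r | Expected patients, clobetasol vs placebo | Chance of p ≤ 0.05, literal clause | Same, common anchor |
|---|---|---|---|
| 10% | 1.7 vs 0 | 2% | 1% |
| 20% | 3.4 vs 0 | 24% | 2% |
| 30% | 5.1 vs 0 | 61% | 2% |

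If the clause covers entry findings only, the difference between the last two columns disappears.

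**The case against.** The strongest reply is that the clause should be read with its neighbours. Findings that have to be documented at baseline and are described as pre-existing are findings present at entry, and a new event on day 7 of placebo is neither. This is probably what was intended, and it stands as the likelier reading. It does not remove the conflict in the operative sentence, which sets its limit by first clobetasol.

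A reader might try to defeat that reply by noting that, for the placebo group, "the OMRS score at the end of the blinded phase/beginning of clobetasol rinse use (day 14) will serve as the baseline". That goes too far. Section 3.1 moves the baseline to day 14 only for the OMRS primary outcome. Appendix G labels Day -7 to 0 as screening and baseline, and Appendix H lists baseline symptoms under enrolment. No section sets a day-14 baseline for adverse events. What remains is that the plan uses the word baseline for two different days and Section 3.3 does not say which it means.

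It is also fair to say that no planned analysis is shown to be affected. The between-arm tests in Section 10.2 concern the OMRS. The adverse-event elements that Appendix H requires in the research database are mainly unexpected related serious events, non-progression deaths and unanticipated problems, so non-serious disease-attributed events are not on that list for either arm. This limits the consequence but does not justify a reporting rule that differs by arm.

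**Conclusion.** The point holds as a wording defect of limited scope. Read literally, Section 3.3 exempts grade 2-3 disease-attributed events for all 14 blinded days on placebo and for none on clobetasol. That conflicts with Section 8.2, and Section 6.1 does not resolve it. The record could therefore be lopsided for this one event class.

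A reader might infer more: that adverse events on placebo generally go unreported, or that the randomised safety comparison is biased by 10-30 percentage points. The documents support neither. The clause covers one class of events, the adjoining sentences point to entry findings, Section 8.2 calls for documentation regardless of cause, and no between-arm safety test is planned. The figures of 1.7-5.1 patients against none rest on an assumed equal rate of 10-30%, complete reporting on clobetasol and complete exemption on placebo. The change is worth making because it is nearly free and removes an arm-dependent rule that could be applied once the arm is known.

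**What to change.** Make three wording changes:
- In Section 3.3, limit the exemption to findings *present before the first dose of study rinse (clobetasol or placebo)*, in place of the present reference to clobetasol.
- In the same section, state that the baseline for adverse events is the Day -7 to 0 assessment in both arms, so that it cannot be confused with the day-14 OMRS baseline of Section 3.1.
- In Section 6.1, to which Section 8.2 refers, give the same start of adverse-event recording for both arms.

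The cost is a short amendment and possibly a few more adverse-event entries for placebo patients. No visit, test or treatment changes. Separate tabulations of adverse events by period would be a reporting preference and are not needed to correct this clause.

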## 3.3.1 **Pre-Treatment Evaluation**

Pre-treatment tests should be performed within 1 month prior to enrollment on the trial unless otherwise stated. Evaluation may be performed as part of enrollment onto NIH Protocol #04-C-0281 entitled: "Prospective Assessment of Clinical and Biological Factors Determining Outcomes in Patients with Chronic Graft-Versus-Host Disease." All attempts will be made to enroll patients on this study; however evaluation may be done as part of any ongoing NCI protocol. A 7-day washout period is required if patients are currently using another oral topical treatment for mouth lesions.

- 1. Optional History and Physical Examination
- 2. NIH global scoring and data collection, including prior and concurrent therapy, (Appendix H)
- 3. Chronic GVHD NIH organ staging
- 4. Assessment of oral GVHD using OMRS and oral cGVHD Clinical Scoring Instrument (Appendix A and Appendix B)
- 5. Numeric rating scales for (0 to 10) for oral pain, oral sensitivity, and oral dryness

## **Appendix C**)

- 6. Oral Global Scale (Appendix D)
- 7. Painometer (POM) Assessment (Appendix E)
- 8. Oral Health Impact Profile- OHIP-14 (Appendix F)
- 9. Hematology: Complete blood counts, with differential and platelet count. Within 72 hours prior to initial evaluation.
- 10. Chemistries: Electrolytes (including sodium, potassium, chloride, CO2, calcium, phosphorus and magnesium), creatinine, BUN, glucose, SGOT, alkaline phosphatase, SGPT, bilirubin, PT/INR and PTT, serum cortisol level and TBNK panel. Within 72 hours prior to initial evaluation.
- 11. FSH, LH, TSH, T4, CMV by PCR, and HSV by PCR.
- 12. Urine or Serum Pregnancy test: For all females of childbearing potential. This test is to be performed within 7 days prior to enrollment on the trial.
- 13. Urine glucose Within 72 hours prior to initial evaluation.
- 14. Biopsy of buccal mucosa (4 mm punch) on patient's right side OR of buccal area with GVHD involvement for histopathological examination.
- 15. Research blood sample collection (18cc)
- 16. Five minute saliva sample, with and without paraffin stimulation
- 17. Short ACTH stimulation test, within 1 week prior to initial evaluation.
- 18. Clinical oral photo series
- 19. Adrenocorticotropic Hormone blood level within 1 week prior to initial evaluation.
- 20. Hemoglobin A1C level

#### **3.3.2** Interim Evaluation

Patients should be evaluated at the NIH 14 days after the start of intervention until Day 28 of active rinse use for the following:

- 1. Optional History and Physical Examination
- 2. Assessment of oral GVHD using OMRS and oral cGVHD Clinical Scoring Instrument (Appendix A and Appendix B)
- 3. Numeric rating scales for (0 to 10) for oral pain, oral sensitivity, and oral dryness (Appendix C)
- 4. Oral Global Scale (Appendix D)
- 5. Painometer (POM) Assessment (Appendix E)
- 6. Oral Health Impact Profile- OHIP-14 (Appendix F)
- 7. Hematology: Complete blood counts, with differential and platelet count

- 8. Chemistries: Electrolytes (including sodium, potassium, chloride, CO2, calcium, phosphorus and magnesium), creatinine, BUN, glucose, SGOT, alkaline phosphatase, SGPT, bilirubin, PT/INR and PTT, cortisol level and TBNK panel.
- 9. Research blood sample collection (18cc)
- 10. Urine glucose
- 11. Five minute saliva sample, with and without paraffin stimulation
- 12. Clinical oral photo series
- 13. Optional pharmacokinetic study
- 14. Hemoglobin A1C level

#### 3.3.3 End of Treatment Evaluation

The following tests and procedures should be performed at the end of scheduled open label treatment period (28 d.) or, if possible, at the time a patient comes off treatment regardless of the reason:

- 1. Optional History and Physical Examination
- 2. Assessment of oral GVHD using OMRS and oral cGVHD Clinical Scoring Instrument(Appendix A and Appendix B)
- 3. Numeric rating scales for (0 to 10) for oral pain, oral sensitivity, and oral dryness (Appendix C)
- 4. Oral Global Scale (Appendix D)
- 5. Painometer (POM) Assessment (Appendix E)
- 6. Oral Health Impact Profile- OHIP-14 (Appendix F)
- 7. Hematology: Complete blood counts, with differential and platelet count
- 8. Chemistries: Electrolytes (including sodium, potassium, chloride, CO2, calcium, phosphorus and magnesium), creatinine, BUN, glucose, SGOT, alkaline phosphatase, SGPT, bilirubin, PT/INR and PTT, HSV by PCR, cortisol level and TBNK panel.
- 9. Urine glucose
- 10. Research blood sample collection (18 cc)
- 11. Biopsy of buccal mucosa (4 mm punch) near baseline biopsy site
- 12. Five minute saliva sample, with and without paraffin stimulation
- 13. Clinical oral photo series
- 14. Short ACTH stimulation test
- 15. Adrenocorticotropic Hormone blood level
- 16. Hemoglobin A1C level

The goal of the day 28 biopsy is to assess microscopic and molecular changes associated with response (or lack thereof) to topical clobetasol for the purpose of potential cGVHD marker development. The primary response variable in this study is clinical grading of cGVHD.

## **3.3.4** Follow-up Evaluation

The following tests and procedures should be performed at the end of the scheduled follow-up period (28 days post end of open label treatment period):

- 1. Optional History and Physical Examination
- 2. Chronic GVHD NIH organ staging
- 3. Assessment of oral GVHD using OMRS and oral cGVHD Clinical Scoring Instrument (Appendix A and Appendix B)
- 4. Numeric rating scales for (0 to 10) for oral pain, oral sensitivity, and oral dryness (Appendix C)
- 5. Oral Global Scale (Appendix D)
- 6. Painometer (POM) Assessment (Appendix E)
- 7. Oral Health Impact Profile- OHIP-14 (Appendix F)
- 8. Hematology: Complete blood counts, with differential and platelet count
- 9. Chemistries: Electrolytes (including sodium, potassium, chloride, CO2, calcium, phosphorus and magnesium), creatinine, BUN, glucose, SGOT, alkaline phosphatase, SGPT, bilirubin, PT/INR and PTT, cortisol level and TBNK panel.
- 10. Research blood sample collection (18cc)
- 11. Five minute saliva sample, with and without paraffin stimulation
- 12. Clinical oral photo series
- 13. Hemoglobin A1C level
- 14. Short ACTH stimulation test (Per PI discretion at day 56 or day 70 depending on subject randomization group) if there is concern for endocrine side-effects)

#### 3.4 DOSE MODIFICATIONS

No dose modifications are expected during this study.

## 3.5 QUESTIONNAIRES

## 3.5.1 Oral Mucositis Rating Scale

Description. The OMRS was constructed through the careful selection of clinical descriptors of oral mucosal changes related to GVHD and also related to BMT. The OMRS was developed "...as a research tool for the comprehensive measurement of a broad range of oral tissue changes associated with cancer therapy" and "to develop an index for assessing acute oral mucositis after BMT". Preliminary development of this scale was performed in studies of chemotherapy toxicities and cGVHD and use of the tool allowed "expedient, efficient, detailed, and reproducible classification of oral changes". The OMRS was used by Schubert, Sullivan, Morton et al. (1984) with 60 patients, who were 180 to 500 days after ABMT, to determine if late oral abnormalities were associated with the presence of cGVHD. Oral manifestations found to be most strongly associated with cGVHD included atrophy and erythema or lichenoid lesions of the buccal and labial mucosa and oral pain.

The tool divides the oral cavity into seven distinct anatomic areas: lips; labial and buccal mucosa; tongue; floor of mouth; palate; and attached gingiva. Each site is further divided into upper and lower (lips and labial mucosa), right and left (buccal mucosa), dorsal, ventral, and lateral (tongue), and hard and soft (palate). Descriptive categories include atrophy, pseudomembrane, erythema, hyperkeratosis, lichenoid, ulceration, and edema. Erythema, atrophy, hyperkeratosis, lichenoid, and edema are rated on scales of 0 to 3 (0 = normal/no change, 1 = mild, 2 = moderate, and 3 = severe change). Ulceration and pseudomembrane are rated on scores based on estimated surface area involved (0 = none,  $1 = \ge 0$  but  $\le 1$  cm^2,  $2 = \ge 1$  cm^2 but  $\le 2$  cm^2, and  $3 = \ge 2$  cm^2). The item pool consists of 91 items for 13 areas of the mouth that are assessed for several types of changes. The score is obtained by summing the scores of all items on the OMRS to yield a total possible score ranging from 0 to 273.

